**Aim 1: To determine the relationship between bolus flow and healthy swallowing physiology.** In Experiment 2, we will collect concurrent videofluoroscopic and physiological measures of swallowing (tongue pressure, electromyography [sEMG], nasal airflow) in healthy adults using barium stimuli across the continuum of liquid consistency. Significance: This will show the impact of consistency on bolus flow through the oropharynx, controlling for the forces used to initiate flow and propel the bolus.

**Aim 2: To compare healthy swallowing physiology for barium versus non-barium stimuli.** In Experiment 4, we will collect physiological measures of swallowing using barium and non-barium stimuli matched for consistency. Significance: This will determine how swallowing behaviors (tongue pressures, sEMG, nasal airflow, tracheal sounds and accelerometry, where captured) differ between barium and non-barium stimuli with matched consistency, enabling us to develop models of flow accounting for these differences.

**Aim 3: To explore the relationship between bolus flow and swallowing physiology in dysphagia.** In a future planned experiment (Experiment 5), we will collect concurrent videofluoroscopy and physiological measures of swallowing in adults with dysphagia using barium stimuli across the continuum of liquid consistency. We will study 5 groups in whom dysphagia is common: stroke; acquired brain injury; oropharyngeal cancer; cervical spine surgery/injury; and neuro-degenerative disease. Significance: This will enable us to identify the boundaries of *ideal* thickening (i.e., *not too thin* and *not too thick*), based on swallowing pathophysiology (altered pressure and force generation capacity).

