## 4. Methods

### *Participants:*

Experiments 2 and 4 will involve the participation of a single sample of participants in the following sub-groups:

i) 40 healthy adults, aged under 60 years old, recruited from the Toronto population at large;

ii) 40 healthy adults, aged over 60 years old, recruited from the Toronto population at large;

Participants will be asked to complete both experiments. Recruitment for Experiment 4 was terminated on July 24 2018 due to technical issues encountered with the equipment that could not be repaired by the manufacturer. The target age ranges for the age sub-groups in Experiments 2 and 4 have been selected based on our previous research, which suggests that significant age-related differences in tongue pressures in swallowing are detectable over the age of 60. We will recruit an equal number of male and female participants within each age-group. Participants of all ethnic and racial groups will be accepted, however adequate comprehension of the English language consent documents will be required.

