- p) Number of swallows for the bolus.

*Data Analysis:*

We will model the impact of bolus consistency on videofluoroscopic measures of pharyngeal bolus flow (i.e., the interval from the bolus passing the mandibular ramus until laryngeal vestibule closure; pharyngeal transit time) and post-swallow residue (Normalized Residue Ratio Scale). The analyses for Experiments 2 and 4 will involve linear mixed model ANOVAs with repeated measures. A path analysis approach will be used to first identify differences in tongue-pressure and submental sEMG measures (amplitude, rise time, decay time) across stimuli. The influence of variations in bolus volume will also be explored using univariate tests, and, if confirmed to be significant, will be used as a covariate in the subsequent statistical models. Similarly, differences in the dependent variables as a function of sex or age (continuous or divided into groups) will be explored first in a univariate fashion, and, if significant, these between-participant factors will be included in the model.

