For Experiment 2, **our main hypothesis is that liquids with similar gravity-flow properties will show similar pharyngeal bolus flow.** Our goal will be to detect differences in bolus flow measures  $\geq 200$  ms as a function of consistency, with a medium effect size (Cohen's  $d \geq 0.5$ ). We hypothesize that the healthy participants in these experiments will use higher amplitudes of tongue pressure and/or submental muscle contraction (sEMG) during oral propulsion of starch-thickened stimuli, thereby achieving a similar outcome for both starch- and gum-thickened liquids in terms of pharyngeal bolus flow. Model fit for different covariance structures will be explored using restricted log likelihood estimation. Age-group (< vs.  $> 60$  years) will be used as a between-groups factor while bolus consistency will be used as the within-participants factor. Sample size calculations have been performed using the data from the PI's previous grant, in which ultrasound measures of the duration of hyoid movement differed by 200-400 ms between age-groups and tongue-pressure amplitudes varied by 10-35 mm Hg depending on the liquid studied. A power calculation shows that 36 participants per group will be needed to detect this difference with 80% power ( $\alpha=0.05$ ). Allowing a margin for attrition, we have therefore planned to enroll  $n=40$  per participant group: total  $N=80$  for Experiments 2 and 4. This sample size will also be adequately powered for Experiment 4 to detect differences  $\geq 10$  mm Hg in tongue-pressure amplitudes.

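### A preliminary significance test on sip volume decides whether the reported consistency effect is total or at equal volume

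*Combined protocol and SAP*

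**What the plan says.** All of this is in Section 4 unless noted.

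- **Model.** "The analyses for Experiments 2 and 4 will involve linear mixed model ANOVAs with repeated measures". Experiment 4 has been terminated, so Experiment 2 is what remains.
- **Volume.** "The influence of variations in bolus volume will also be explored using univariate tests, and, if confirmed to be significant, will be used". The use meant is adjustment in the later models. The form, level and outcome of the preliminary test are not given.
- **Sip size.** Under Data Collection Procedures, participants take sips of natural size from 40 ml cups. Each cup is weighed before and after, so volume is measured but not fixed.
- **Sex and age.** These are screened in the same way: "if significant, these between-participant factors will be included in the model". Age may be continuous or grouped.
- **Age again.** The Experiment 2 paragraph says that age-group, split at 60 years, "will be used as a between-groups factor while bolus consistency will be used as the within-participants factor". No condition is attached.
- **Target.** The main hypothesis reads "our main hypothesis is that liquids with similar gravity-flow properties will show similar pharyngeal bolus flow". The goal is to detect differences of at least 200 "ms as a function of consistency, with a medium effect size", d of at least 0.5. Section 3, Aim 1, describes the consistency effect as "controlling for the forces used to initiate flow and propel the bolus". Volume is not mentioned in either place.
- **Recruitment.** "We will recruit an equal number of male and female participants within each age-group".

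**The concern.** Volume is fixed by the participant after the stimulus is given, so it may lie on the path from consistency to bolus flow. A model without volume then answers how flow differs when people drink each liquid as they naturally would. A model with volume answers how flow would differ at the same sip size. Both are legitimate questions, but they are different ones, and the plan lets a preliminary p-value choose between them. Since the rule can be applied outcome by outcome, the choice could differ between the timing measures and residue, and results in one table would not be comparable.

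The interval from the chosen model also ignores the selection step, so its 95% label need not hold for the effect the reader believes is being reported.

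A smaller matter is the gating of age and sex. The general text makes age conditional and the Experiment 2 paragraph makes it unconditional. Sex is balanced by design yet can drop out of some models and not others.

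**Working it through.** The plan gives no figure for sip volume or for its effect on timing, so there is nothing of its own to reproduce here. The numbers below are illustrations on stated assumptions.

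**1. Gap between the two effects.** Total effect = direct effect − (effect per mL × fall in volume from thin to extremely thick). Take a direct effect of 200 ms (the plan's goal) and assume 10 ms/mL.

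- 4 mL fall: gap 10 × 4 = 40 ms; total 200 − 40 = 160 ms.
- 8 mL fall: gap 10 × 8 = 80 ms; total 200 − 80 = 120 ms.

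That is 20-40% of the 200 ms goal. At 5 ms/mL the gap halves to 20-40 ms. With no fall, or no effect per mL, it is zero.

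**2. What the gate does when volume matters.** Simulation: 80 participants × 9 stimuli × 2 presentations = 1,440 boluses. Assumed: per-bolus SD 400 ms (200/0.5, an inference; the documents state no SD), within-participant correlation 0.3-0.7, volume SD 4 mL between and 2 or 4 mL within participants, 10 ms/mL, 4-8 mL fall, 200 ms direct effect. The volume test is two-sided at 5%, with consistency already in the model.

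| Quantity | Range over settings |
|---|---|
| Gate opens | 63-100% |
| Mean unadjusted contrast | 118-161 ms |
| Mean adjusted contrast | 198-201 ms |
| Gated 95% interval covers the total effect | 8-82% |
| Gated 95% interval covers the equal-volume effect | 74-96% |

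The lowest coverage of the total effect arises where the gate opens almost always, so that the equal-volume effect is in practice what is reported. That is harmful only if the total effect was meant, which the plan does not say.

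**3. A case where neither effect is covered.** A second, standardised simulation used one contrast of two consistencies, 72 participants, SD 1 for both the residual and the volume difference, and no effect at equal volume.

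| Volume slope | Mean volume shift | Gate opens | Covers total | Covers equal-volume |
|---|---|---|---|---|
| 0.2 | 0.5 SD | 38% | 89% | 89% |
| 0.2 | 1 SD | 38% | 79% | 74% |
| 0.3 | 0.5 SD | 69% | 80% | 89% |
| 0.3 | 1 SD | 70% | 58% | 76% |

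Always adjusting kept the error rate for the equal-volume effect at 4.7-5.6%. Never adjusting is valid for the total effect by theory.

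**4. When volume has no effect.** The gap is zero and both models are unbiased (means about 199-204 ms in the setting of step 2 with 0 ms/mL). A false opening raises the standard error of the end-to-end contrast by about 4-50%. The test opens falsely in 3-6% of runs if consistency is in it. If volume is the only predictor, it opens in 66-100% of runs, because volume then stands in for consistency.

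**5. Starch versus gum at the same level.** An assumed 1-2 mL difference at 5-10 ms/mL gives 5-20 ms, or 2.5-10% of 200 ms. One video frame at 30 frames/s is 1000/30 ≈ 33 ms.

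**6. Sex gate.** Two-sample t-test on participant means, 40 v 40, 18 boluses each, effective d = d/√((1+17ρ)/18). For ρ from 0.3 to 0.7, a true d of 0.5 is screened out 3-26% of the time. A d of 0.3 is screened out 38-65% of the time and overstated 1.3-1.7-fold when kept. This concerns the sex estimate itself, not the consistency contrast.

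**The case against.** **The test may include consistency.** Univariate can mean one dependent variable rather than one predictor; it could even mean comparing volume across stimuli. This stands. A reader might infer that the gate will usually open falsely (66-100%) and distort the result. The documents do not support that: the figure depends on the one-predictor reading, and a false opening leaves the estimate unbiased. The point survives because step 2 already puts consistency in the test.

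**Exploring volume is only exploratory.** This does not stand. The same sentence lets the result decide the content of the later models.

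**The main hypothesis is hardly touched.** Largely right. The starch-gum comparison is affected only if sip volume differs between agents at the same level, and the assumed gap there is below one video frame. The wider comparison across consistency levels, which carries the 200 ms goal, is more exposed.

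**Age is settled, and sex is not a study question.** Mostly right. The specific Experiment 2 text can reasonably be read as governing. No aim or hypothesis concerns sex. A reader might infer that dropping age or sex biases the consistency effect; in balanced within-participant data it does not.

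**The SD is not the plan's.** Correct. 400 ms is inferred from 200 ms and d = 0.5. It could equally be the SD of paired differences, and a two-sample reading of 36 per group at 80% power implies about 299 ms. The SD was not varied, and the simulation in step 2 uses the 80 enrolled rather than 72 evaluable, so its ranges do not span all the uncertainty.

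**Conclusion.** The concern holds for volume. The plan leaves the target of the consistency effect open and lets an unspecified preliminary test settle it. If volume shifts with consistency and also affects timing, the two candidate effects differ and the gated interval is not a 95% interval for at least one of them. On the assumed values the gap is 40-80 ms, and coverage of the total effect falls well below 95% even under the more favourable reading of the test.

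The size is conditional. No volume data are given, so the practical gap may be zero; if volume has no effect, the cost is precision alone. The documents do not support saying that the main result is biased or that the starch-gum hypothesis is compromised. The conflict on age and the gate on sex are secondary: they affect the age and sex estimates and the consistency of models across outcomes, not bias in the within-participant contrast. This should be corrected before analysis; it does not threaten the design.

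**What to change.** 1. Delete the significance gate on volume.
2. State before analysis whether the primary consistency effect is total (no volume covariate) or at equal volume (volume always in the model). The choice is the sponsor's. Removing the gate does not in itself mean that volume must be adjusted for.
3. Report the other effect as a fixed secondary analysis for every outcome, whatever the p-values.
4. Reconcile the general Data Analysis text with the Experiment 2 paragraph, so that age-group (split at 60) is always in the Experiment 2 model, and include sex without a gate.

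The cost is a change of wording, one extra model per outcome on volumes already planned to be measured, and 2 degrees of freedom for the age-group and sex main effects. No change to sample size or data collection is needed.

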Participants will be asked to swallow the barium stimuli developed in Experiment 1 (9 in total) in videofluoroscopy, with concurrent measurement of nasal airflow. Videofluoroscopy will be performed at maximum temporal resolution (30 pulses/second) and captured at 30 frames/second. Each stimulus will be presented twice, in a randomized block design.

Participants will be allowed to take natural sized sips of each stimulus from cups containing 40 ml. Cup weights before and after each sip will be taken on a digital balance so that sip volume and mass can be calculated.

Experiment 4: Experiment 4 was terminated on July 24 2018 due to technical issues encountered with the equipment that could not be repaired by the manufacturer.

*Data Processing:*

Signals collected from the participants (which may include tongue-pressure, sEMG, nasal airflow, tracheal sounds and accelerometry waveform data) will be segmented using an automatic segmentation algorithm developed previously in the PI's lab. Similarly, the videofluoroscopy recordings will be spliced into single bolus clips and the audio channel will be muted to remove cues that might bias rating. Blinded videofluoroscopy rating will then be performed in duplicate by trained raters in the [name] Lab following established procedures (see Appendix E). Discrepancies between raters will be flagged and resolved at consensus meetings, as required. These procedures will yield a large number of parameters for each swallow, as listed below:

- a) Peak tongue-pressure amplitude (in mm Hg);
- b) Rise-time to peak tongue-pressure (in ms);
- c) Decay-time for tongue-pressure (in ms);
- d) Tongue-pressure area-under-the-curve;
- e) Peak sEMG amplitude (in  $\mu$ V);
- f) Rise-time to peak sEMG amplitude (in ms);
- g) Decay-time for sEMG (in ms);
- h) sEMG area-under-the-curve;
- i) Duration of apnea (ms);
- j) Breathing pattern pre- and post- swallow;
- k) Bolus transit time from ramus of mandible to vallecular pit (in ms);
- l) Bolus dwell time in pharynx from ramus of mandible to laryngeal vestibule closure (in ms);

- m) Pharyngeal bolus transit time from ramus of mandible to upper esophageal sphincter opening (in ms);
- n) Bolus transit time from ramus of mandible to tail exiting the upper esophageal sphincter (in ms);
- o) Amount of residual left behind in the valleculae and pyriform sinuses after the initial swallow (measured using the Normalized Residue Ratio Scale;

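### Experiment 2's main hypothesis is that matched starch- and gum-thickened liquids flow similarly, but the plan has no criterion for similarity and no named starch-gum contrast for bolus flow

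*Combined protocol and SAP*

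**What the plan says.** All of this is in Section 4 (Methods) unless noted.

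- **Hypothesis.** Data Analysis gives the Experiment 2 main hypothesis as "liquids with similar gravity-flow properties will show similar pharyngeal bolus flow". It then expects participants to push harder on starch-thickened stimuli, "thereby achieving a similar outcome for both starch- and gum-thickened liquids in terms of pharyngeal bolus flow".
- **Statistical goal.** The sentence after the main hypothesis reads "Our goal will be to detect differences in bolus flow measures" of at least 200 ms as a function of consistency, with Cohen's d of at least 0.5.
- **Model.** "The analyses for Experiments 2 and 4 will involve linear mixed model ANOVAs with repeated measures". Age group is the between-groups factor, and "bolus consistency will be used as the within-participants factor".
- **Path analysis.** Its one written step is to "first identify differences in tongue-pressure and submental sEMG measures (amplitude, rise time, decay time) across stimuli". No bolus-flow step is written. The current Experiment 2 procedures also list tongue pressure only for maximum presses and saliva swallows, not for the barium swallows.
- **Design.** The Stimuli subsection gives one thin and eight thickened liquids (four gum, four starch), which makes four matched pairs. "Each stimulus will be presented twice, in a randomized block design".
- **Meaning of consistency.** Section 3 describes the starch- and gum-thickened liquids as five consistencies.

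**The concern.** The hypothesis and the goal concern different comparisons. The hypothesis compares liquids matched on gravity flow and expects little or no difference. The goal compares liquids that differ in consistency and looks for a difference. Finding or not finding a consistency effect says nothing about whether starch and gum at the same level flow alike.

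If consistency has five levels, starch and gum share a level and their difference is averaged away. If the nine stimuli are coded separately, the model will give a starch-gum estimate and interval, but no rule says how to read them. A non-significant difference could then be taken as support for similarity, or a small significant one as evidence against it. Either reading would depend on how noisy the data are as well as on how large the difference is.

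**Working it through.** **1. What the plan's own sample size covers.** The plan states 36 per group for 80% power at alpha 0.05. A two-group comparison at d = 0.5 needs 63 per group (normal approximation) or 64 (t test). A paired test needs 34 in total. Exactly 36 per group results for a between-group comparison averaged over nine stimuli with correlation 0.5, using the variance factor (1 + 8 × 0.5)/9 = 0.556, but the plan states no such assumption. On every route the figure powers a test of difference. Its stated basis is prior data on hyoid movement by age group and tongue pressure by liquid, not starch-gum bolus flow.

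**2. Inputs for the missing comparison.**

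- n = 72 completers (36 × 2), because the contrast is within person.
- No SD is given. If 200 ms corresponds to d = 0.5, a single-swallow SD is 200/0.5 = 400 ms. This is an assumption.
- Within-person correlation r = 0.5, 0.25 or 0 (assumed), so the within-person variance is w = 400² × (1 − r).
- Two presentations are averaged. If a share f of w is person-by-stimulus variation, the paired-difference SD = √[2 × (f·w + (1 − f)·w/2)].

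| f | r = 0.5 | r = 0.25 | r = 0 |
|---|---|---|---|
| 0 | 283 | 346 | 400 |
| 0.5 | 346 | 424 | 490 |
| 1 | 400 | 490 | 566 |

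Example: f = 0 and r = 0.5 give w = 80,000 and √(2 × 40,000) = 283 ms. If d was instead meant for the paired difference itself, the SD is 400 ms directly.

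**3. Chance of a non-significant result** (paired t, two-sided 0.05, noncentrality = true difference × √72 / SD), and the 90% confidence-interval half-width = 1.667 × SD/√72:

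| SD (ms) | true 200 ms | true 150 ms | true 100 ms | half-width (ms) |
|---|---|---|---|---|
| 283 | <0.1% | 0.7% | 16% | 56 |
| 346 | 0.2% | 5% | 32% | 68 |
| 400 | 1.3% | 12% | 45% | 79 |
| 500 | 8% | 29% | 61% | 98 |
| 566 | 16% | 40% | 68% | 111 |

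The opposite misreading is also possible: at SD 283, a true 50 ms difference is significant about 32% of the time.

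**4. Whether an explicit similarity rule is feasible.** Power of two one-sided tests (each at 0.05), per level, true difference 0, n = 72:

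| SD (ms) | ±200 ms | ±150 ms | ±100 ms |
|---|---|---|---|
| 283 | ~100% | 99.5% | 82% |
| 346 | 99.9% | 95% | 57% |
| 400 | 98.9% | 87% | 35% |
| 500 | 91% | 62% | 6% |
| 566 | 82% | 44% | <1% |

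Power per level stays at 80% or more up to an SD of about 574, 431 and 287 ms for the three margins. Requiring all four levels to pass, taken as independent (power⁴), gives 98 / 83 / 57 / 15 / 4% for ±150 ms and about 44 / 10 / 1.5 / 0 / 0% for ±100 ms, in the row order of the table.

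**The case against.** The starch-gum comparison is not absent from the plan. It is named as an expectation for bolus flow, the design supplies four matched pairs with two presentations each, and the word first in the path-analysis sentence implies a later step. Coding all nine stimuli is not excluded. That stands, so the missing contrast is under-specification rather than a demonstrably wrong model.

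No text says that non-significance will be read as similarity. In the Experiment 4 hypothesis the authors recognise that expected intermediate values may fail to reach significance. The harm is therefore conditional. At the one difference the plan names, 200 ms, the miss rate is at most 1.3% for SDs up to 400 ms. The larger rates come from 100 and 150 ms, which the plan does not call important, or from larger SDs. That also stands, and the tables illustrate rather than measure the defect.

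It can also be argued that a physiological study in healthy adults needs only estimates and intervals, not a formal equivalence test. But the protocol declares a main hypothesis and sizes a sample. Without a stated size of difference that counts as similar, what supports that hypothesis would be decided after the data are seen. None of these points supplies the missing criterion.

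**Conclusion.** The concern holds. The main hypothesis is one of similarity between matched liquids, while the only written bolus-flow analysis seeks differences between consistencies. No criterion for similarity is given and no starch-gum flow contrast is named. This conclusion rests on the text alone.

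The numerical size is conditional on the assumed SDs, 72 completers and a paired comparison at one level. Under those assumptions, treating non-significance as similarity would pass a true 100 ms difference 16% to 68% of the time. The defect is the missing contrast and decision rule. It is not shown that the sample is too small or that the mixed model is unsuitable. It should be fixed before the bolus-flow data are analysed.

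**What to change.** - **Name the contrast.** In the bolus-flow model, include a thickener-by-level term for the eight thickened stimuli, or a nine-level stimulus factor. Use both presentations, with participant and participant-by-stimulus random effects so that two swallows of one stimulus are not treated as independent.
- **Set the rule.** Estimate starch minus gum at each of the four thickened levels with a 90% confidence interval. Declare similarity at a level only if the interval lies wholly within a justified margin fixed before the bolus-flow data are analysed. Call the level different if the interval lies wholly outside the margin, and inconclusive otherwise. The 200 ms figure was set for differences between consistencies, so it is at most an upper bound for the margin.
- **Say how the four levels bear on the hypothesis.** Allow level-by-level conclusions, since requiring all four to pass may be out of reach with a tight margin.
- **Say which flow measure carries the conclusion.** Data Analysis names two: "the interval from the bolus passing the mandibular ramus until laryngeal vestibule closure; pharyngeal transit time".
- **Keep the existing ANOVA** for the effect of consistency.

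The cost is analysis wording and a justified margin, with no new participants or measurements. The downside is that similarity can no longer be claimed from a non-significant p-value. Whether a margin near 100 ms is workable at this sample size depends on an SD the documents do not give.

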- a) An intake questionnaire noting age, sex, ethnicity and race data and confirming eligibility based on the absence of reported exclusion criteria.
- b) During the intake process, we will ask to review a list of conditions that could alter the results of the research study and identify whether any of these conditions apply. This disclosing the use of any medications that they are currently taking, in order to allow us to control for the possible influence of medication on oral sensory and motor function. Medications do not qualify as the basis for exclusion. However, it is important for us to collect information regarding the use of benzodiazepines and neuroleptic medications that are known to have possible effects on swallowing, particularly with respect to causing xerostomia (dry mouth).

*Signals to be collected from each participant:*

- c) Tongue-pressure waveform data, using the hand-held Iowa Oral Performance Instrument (IOPI) will be collected at the anterior position during 3 anterior maximum presses and 3 saliva swallows.
- d) Nasal airflow collected using nasal cannula and registered on the KayPENTAX Swallowing Signals Lab during swallows.
- e) A videofluoroscopy recording of swallowing involving a pulse rate of 30 pulses per second and video capture at 30 frames per second.

*Data Collection Procedures:*

Experiment 2: Prior to data collection, a nasal cannula will be placed around the participant's head with flexible prongs resting in their nostrils to measure airflow.

A single use disposable tongue bulb for the hand-held Iowa Oral Performance Instrument (IOPI) will be placed inside the participant's mouth. Tongue pressure signal will be collected at the anterior position during 3 anterior maximum presses and 3 saliva swallows.

[figure not shown]

Image 1. Tongue pressure sensors.

Following sensor attachment, the participants will be seated on a chair inside the fluoroscopy unit. The video output line from the fluoroscopy unit and the nasal cannula will then be connected to the KayPENTAX Digital Swallow Workstation Swallowing Signals Lab equipment,

which is located on a properly insulated cart with an uninterrupted power supply and isolation transformer.

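### N=80 is still said to power Experiment 4's tongue-pressure comparison, but that experiment was terminated, and Experiment 2 as now described provides for neither tongue pressure nor sEMG during the stimuli

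*Combined protocol and SAP*

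**What the plan says.** **Power.** Section 4, Data Analysis, derives 36 per group at 80% power and alpha 0.05, raises this to 40 per group for attrition, and applies the total of 80 to Experiments 2 and 4. It continues: "This sample size will also be adequately powered for Experiment 4 to detect differences" of 10 mm Hg or more in tongue-pressure amplitude.

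**Aims.** Section 3, Aim 1, says that in Experiment 2 "we will collect concurrent videofluoroscopic and physiological measures of swallowing (tongue pressure, electromyography [sEMG], nasal airflow) in healthy adults", so as to show the effect of consistency on flow while "controlling for the forces used to initiate flow and propel the bolus". Aim 2 reads: "In Experiment 4, we will collect physiological measures of swallowing using barium and non-barium stimuli matched for consistency".

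**Status of Experiment 4.** Section 4, Participants, says: "Participants will be asked to complete both experiments". The next sentence says: "Recruitment for Experiment 4 was terminated on July 24 2018 due to technical issues encountered with the equipment". Under Data Collection Procedures, the Experiment 4 entry consists only of a statement that the experiment itself was terminated on that date. Section 7, Compensation, lists two appointments, intake and Experiment 2.

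**Experiment 2 as now described.** "Tongue pressure signal will be collected at the anterior position during 3 anterior maximum presses and 3 saliva swallows". Tongue pressure comes from a hand-held device. For the workstation, "The video output line from the fluoroscopy unit and the nasal cannula will then be connected to the KayPENTAX Digital Swallow Workstation". The list of signals to be collected has three entries: tongue pressure in those tasks, nasal airflow and videofluoroscopy. The barium stimuli are then swallowed with nasal airflow as the only concurrent signal.

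**The concern.** The procedures were updated after the equipment failure, but the sample-size and analysis text was not. Two things follow.

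First, the power sentence attaches N=80 to an experiment that stopped early, with no statement of how many completed it.

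Second, several analyses still need tongue pressure or sEMG for each stimulus, and the remaining experiment does not provide for those signals while the stimuli are swallowed. These analyses carry the mechanism. The plan expects starch- and gum-thickened liquids to flow alike because people push harder on the starch ones. Without force measured during those swallows, similar flow can be observed but the proposed reason cannot be tested.

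If the text stays as it is, the tongue-pressure and sEMG comparisons look sized at N=80 when they can rest only on an undeclared subset, and who belongs to that subset could be settled after the data are seen.

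**Working it through.** **1. Can the 10 mm Hg statement be reproduced?** No. The plan gives no SD, contrast, sidedness or numerical power for it. It says only that tongue pressure varied by 10-35 mm Hg across liquids in earlier work, which is a range of differences and not an SD. What can be shown is what the statement would require if all 80 had completed. With two-sided alpha 0.05, 80% power and t-based calculations, the largest tolerable SD is 10 divided by the detectable standardised difference:

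| Contrast (assumed) | n | Largest SD, mm Hg |
|---|---|---|
| Between age groups | 36 per group | 14.9 |
| Between age groups | 40 per group | 10 / 0.634 = 15.8 |
| Within person | 72 pairs | 29.9 (SD of differences) |
| Within person | 80 pairs | 31.5 (SD of differences) |

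Over an assumed range of SDs:
- Between groups, 40 per group (normal approximation): power is 0.85, 0.61, 0.43 and 0.32 at SD 15, 20, 25 and 30. For example, at SD 20, 10 / (20 × √(2/40)) = 2.236; 2.236 − 1.960 = 0.276; Φ(0.276) = 0.61.
- Within person, 80 pairs: power is 0.99, 0.94, 0.84 and 0.71 at SD of differences 20, 25, 30 and 35.

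So even at full enrolment the statement depends on unstated inputs. It also depends on n. If, purely for illustration, 40 people had completed a within-person contrast, the largest tolerable SD of differences would fall from 31.5 to 22.0. The actual number is not in the document, so achieved power cannot be computed.

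**2. How many stimulus swallows carry a force signal under the current Experiment 2 procedure?**
- Stimulus swallows per person: 9 stimuli × 2 presentations = 18.
- Tongue-pressure tasks: 3 presses + 3 saliva swallows = 6, none with a stimulus.
- sEMG: not in the signal list.
- Stimulus swallows with tongue pressure or sEMG: 0 of 18.

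**3. Which outputs lose their source?** Data Processing and its continuation list 16 per-swallow outputs, (a) to (p).
- (a)-(d), tongue pressure: 4 outputs; saliva swallows only.
- (e)-(h), sEMG: 4 outputs; no listed signal.
- (i)-(j), respiration: from nasal airflow.
- (k)-(p), flow, residue and number of swallows: from videofluoroscopy.

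That leaves 4 + 4 = 8 of 16 with no by-stimulus source.

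**4. Which planned analyses depend on those outputs?**

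| Planned item | Needs | Current procedure gives |
|---|---|---|
| Path analysis across stimuli (Data Analysis) | Tongue pressure and sEMG by stimulus | Neither |
| Higher force for starch-thickened stimuli (Data Analysis) | Tongue pressure or sEMG by stimulus | Neither |
| Aim 1 adjustment for force | Force in the same swallow as the flow measure | Person-level presses and saliva swallows only |
| Aim 2 and Experiment 4 hypotheses | Experiment 4 recordings | No procedure; only participants studied before termination |
| Bolus flow by consistency (Experiment 2 main goal) | Videofluoroscopy by stimulus | Available |

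**The case against.** The strongest reply is that this is an incompletely amended plan and not a live claim of achieved power. The termination is disclosed twice with its date and reason, so anyone who reads all of the Methods knows that Experiment 4 stopped early. Data Processing is worded conditionally about which signals are present. Aim 2 has a similar qualifier, though it may cover only tracheal sounds and accelerometry. Equipment failure is unrelated to results, so prespecified hypotheses remain prespecified at a smaller n. The number who completed is normally reported with results.

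Much of this stands, and it rules out several inferences that a reader might draw:

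- **That no tongue-pressure or sEMG data exist for the stimuli.** Not supported. The Participants text stops recruitment only, and earlier participants may have recordings. The 0 of 18 describes the current procedure, not the data in hand.
- **That the equipment budget shows such data were recorded.** Also not supported. The budget justification requests funds for the workstation and does not report recordings.
- **That sEMG was never recorded.** The documents support only that it is absent from the current signal list. The adhesive-allergy exclusion mentions the chin and neck, and the budget still includes EMG sensors. Either may be a leftover.
- **That no adjustment for force is possible.** Presses and saliva swallows could supply a person-level covariate, although none is planned. What is lost is adjustment by swallow.
- **That the affected analyses must be relabelled exploratory.** That does not follow from an equipment failure.

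What the reply does not answer is the sentence itself, which is current text and assigns N=80 to Experiment 4. Nor does the termination notice say whether the path analysis, the starch hypothesis or Aim 1's force adjustment continue, and these also bear on Experiment 2.

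**Conclusion.** The contradiction holds. The current design does not support the stated N=80 power for Experiment 4, and a block of planned analyses has no by-stimulus input under the current Experiment 2 procedure. The conclusion rests on the text of sections 3, 4 and 7 alone; the SD ranges above are illustrative and it does not depend on them.

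Aim 2 and the Experiment 4 hypotheses can rest only on participants studied before the termination, in unstated number. The mechanistic part of Aim 1 has the same limit.

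A reader might go further and infer that Experiment 2 as a whole is undermined, or that 80 is the wrong size for it. This point supports neither. The bolus-flow comparison uses videofluoroscopy, which is still collected for every stimulus, and no position is taken here on whether N=80 is right for Experiment 2.

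**What to change.** 1. Delete the Experiment 4 power sentence, or restate it as the tongue-pressure difference detectable with the number who completed Experiment 4, giving the SD and contrast used. Stop attaching N=80 to Experiment 4.
2. Restrict the path analysis across stimuli, the starch hypothesis and the Experiment 4 comparisons to participants with tongue-pressure or sEMG recordings during the stimuli. Report that n and the resulting precision. If there are none, remove these analyses.
3. Align Aims 1 and 2, the Participants statement about completing both experiments, the output list in Data Processing and the hypotheses in Data Analysis with the signals actually recorded.

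The cost is rewording and a count of existing recordings, with no extra enrolment. The downside is that Aim 2 and the force-related part of Aim 1 are reported at a smaller n or dropped.
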